## 8.12. Questionnaires and Structured Interviews

## 8.12.1. Dietary Questionnaires, Records, and Interviews

## 8.12.1.1. Maternal Nutrition

Measurement of maternal diet will be collected by means of a short food frequency questionnaire (FFQ), which concentrates on the intakes of fish and fish products, milk and milk products, and cereal and cereal products during the eighth month of pregnancy (for Finland and Germany) (Erkkola et al., 2001). The eighth month is considered the appropriate reference month in these countries because mothers start their maternity leave in the ninth month. Therefore, the eighth month might more accurately reflect the pregnancy diet than the ninth month because of the change in lifestyle that would occur when one went on maternity leave. In the United States and Sweden, this type of maternity leave does not occur, and therefore the reference month will be the ninth month for the collection of the food frequency questionnaire. The use of dietary supplements is asked as well as source of drinking water. The height of the mother is inquired as well as the weight before pregnancy and the weight gain during pregnancy.

## 8.12.1.2. Dietary study in children

In addition to food consumption, dietary habits of the participating infants (e.g. feeding pattern) will be assessed by mailed questionnaire that is to be completed prior to the first clinic visit, a structured interview at each clinic

visit, and records kept by the mother in the TEDDY Book (see Table 2 and section 8.11.2). The duration of total and exclusive breastfeeding, age at introduction of various foods during the first 2 years of life, type of infant formulas used, source of drinking water (local waterworks, bottled water, private wells), elimination diets, and use of dietary supplements will be recorded.

Primary caretakers (usually mothers) will be trained during the three-month clinic visit to keep 3-day food diaries of the child's dietary intake at 3 month intervals during the first year of life and biannually thereafter. A 24-hour recall of the child's diet will be obtained at the first (3-month) visit. The collection of this 24-hour recall will have two purposes: 1) to assist in *training* the primary caretakers in what types of food items they will need to record when they complete the 3-day diet records; and 2) the dietary data from the 24-hour recall will be used to reflect the infant's diet at 3 months of age. The first 3-day food diary will be given to the primary caretaker at the threemonth visit after training. The primary caretaker will be instructed to fill out the 3-day food diary directly prior to the next clinic visit (in this case the 6 month clinic visit), so that they can bring the completed record with them (Gregory et al., 1995). At each clinic visit, the diet records will be reviewed by trained study personnel with the primary caretaker.

In August 2018, the collection protocol was changed so as to continue to collect 3 day diet records every 6 months from subjects who are single or multiple persistent confirmed autoantibody positive (even if the subject reverts to autoantibody negativity) and to stop 3 day diet record collections on all other subjects after the 10 year visit. Should a subject be deemed single or multiple persistent confirmed autoantibody positive after the 10 year visit, the 3 day diet record collection will be restarted at the next visit. This will provide a complete dataset on all subjects up through 10 years of age and continued collection on persistent confirmed autoantibody positive subjects through the end of the study. Continued data collection on persistent confirmed autoantibody positive individuals will enable the TEDDY study to explore the role of diet, and dietary changes, through early adolescent years, on progression to T1D. It has been noted that the diet of individuals in this 10-15 year age interval is changed as compared to the diet at younger ages. These data will enable TEDDY to include these dietary patterns in assessments of T1D risk along with other exposures and changes occurring during the peripubertal period to include energy intake, energy expenditure, growth, hormonal changes and glucose demand. Epidemiological data points to increased T1D incidence during this period, TEDDY has also observed a declining rate of conversion from autoantibody negative to autoantibody positive (i.e., lower incidence of seroconversion during this age range). This reduces the statistical power to see an effect of dietary changes during the 10-15 year age range. Coupled with a lower compliance rate, as compared to families completing the 3 day diet record whose child is persistent confirmed

autoantibody positive, it seems prudent to reduce the burden on families and clinic staff by discontinuing data collection after 10 years of age for families whose child is autoantibody negative. TEDDY will have a complete data set on this population through age 10 years so it will be able to address the contribution of diet in the cumulative incidence of islet cell autoimmunity up to this age.

Research personnel of all TEDDY countries need continuous training for checking of food diaries. Standardization will be done at all levels of the study: training of research personnel, advice material, checking of diaries, food data entry, food composition databases, and food and nutrient calculations. Food databases to be used in the TEDDY countries will be compared to assess which dietary factors are comparable (De Henauw et al., 2002). All food diaries will be entered continuously at each respective center/country.

Foods	Nutrients and Energy	Other Nutritional Factors
Cows milk	Energy intake	Nitrates, nitrites and N-nitroso
		compounds
Cereals, wheat (gluten)	Proteins	Patulin
Soy	Vitamins C, D and E	Bafilomycin
Meat	Nicotinamide	Increased weight and/or height gain
		(fetal period, infancy, childhood)
Coffee and tea	n-3 fatty acids	
Breast milk	Zinc	
Cod liver oil	Carotenoids and selenium	

Table 4. Nutritional Factors of Interest in the TEDDY Study

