### 8.11. Physical Activity Assessment

Measurement of physical activity will be used to examine the effect of physical activity and test the accelerator and overload hypotheses on T1D development in the TEDDY cohort. Assessment of physical activity will be used to test the following hypotheses: (1) low rates of physical activity, high body mass index, a pattern of high caloric intake in a single meal, and high consumption of foods with a high glycemic index are associated with the development of persistent anti-islet autoantibodies in genetically at-risk children, and (2) low rates of physical activity, high body mass index, a pattern of high caloric intake in a single meal, and high consumption of foods with a high glycemic index are associated with more rapid progression to T1D in children who have developed persistent anti-islet autoantibodies.

On an annual basis, beginning at 5 years of age, TEDDY participants will wear the Actigraph GT3X accelerometer for 7 consecutive days (including 2 weekend days) in order to generate adequate valid data. Accelerometers are small light-weight devices that measure change in velocity over time. When worn on the hip, lower back, or ankle, they are used to quantify the volume and intensity of movement in 1-, 2-, or 3-planes. They can also be worn on the wrist to assess sleep patterns and efficiency (Oliver 2007).

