To maximize compliance, families will receive in-person demonstrations on how to wear and use the accelerometer during the TEDDY visit immediately prior to the specific TEDDY visit targeted for accelerometer data collection. One month prior to the TEDDY visit targeted for the accelerometer data collection, the accelerometer will be mailed to families with instructions to begin using the device two days before the three day diet recording period and for two days after. A follow-up reminder telephone call will be used to prompt device use and to answer any questions. All families will be asked to return the accelerometer at their next TEDDY visit and will be given a pedometer as a "thank you" for the prompt return of the device. For those who forget to bring the accelerometer to the TEDDY visit, mailing envelopes and reminder phone calls will be used to prompt return of the accelerometer.

When the children reach 8 years of age, TEDDY will reference reported epidemiological surveys (Sallis 1006, Kimm 2000, CFC YRBSS) and develop a comprehensive questionnaire on child activities to use in conjunction with the objective accelerometer data collection.

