The issue of "double diabetes", i.e. coexistence of islet autoimmunity, insulin resistance and beta cell failure will likely be more important in TEDDY population than rare forms of diabetes, such as MODY. While presence of islet autoantibodies in TEDDY participants diagnosed with diabetes will be sufficient to classify those cases as type 1A diabetes, markers of insulin resistance (e.g., higher BMI, higher fasting insulin or C-peptide levels or HOMA (Matthews et al., 1985) will have to be included as potential confounders in the analyses of time to progression to diabetes. The "Accelerator Hypothesis" (Wilkin, 2001) argues that autoimmune destruction of beta cells is accelerated by weight gain and insulin resistance, thus type 1A diabetes may develop faster in children who are overweight. In addition, some suggested that higher BMI may be associated with increased prevalence and titer of islet autoantibodies, especially GAD (Weets et al., 2001; Rolandsson et al., 1999).

To diagnose diabetes, the following ADA Criteria must be met on two occasions (unless criteria 4 is present):

- 1. Casual (any time of day without regard to time since last meal) plasma glucose >= 200 mg/dL, if accompanied by unequivocal symptoms (i.e. polyuria, polydipsia, polyphagia, and/or weight loss.)
- Or

2. Fasting (no caloric intake for at least 8 hours) plasma glucose  $\ge 126 \text{ mg/dL}$ Or

- 3. 2-hour plasma glucose >=200 mg./dL oral glucose tolerance test (OGTT). Glucose dose is determinant on body weight to a maximum of 75 grams.
- Or
- 4. Unequivocal hyperglycemia with acute metabolic decompensation (i.e. ketoacidosis)

Unless criterion 4 is present or the fasting glucose is >=250 mg/dL (at the bedside or in the local laboratory on the day of testing), it is preferred that at least one of the two testing occasions involve an oral glucose tolerance test (OGTT). If the first criterion met is #3, i.e. by the 2-hour OGTT value, the OGTT should be repeated within 60 days. It is essential that every effort be made to obtain the necessary tests to establish the diagnosis of diabetes. Subjects will be instructed to eat a balanced diet in the days leading up to the OGTT.

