#### OGTT alert:

All study participants found to be positive for two or more islet autoantibodies will be asked to undergo standard OGTT every six months at the time of their regular TEDDY visit. Details for these procedures are outlined in the study Manual of Operations.

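### From age 5, the diary timing, accelerometer wear window and device return leave 5 of 7 planned wear days; separately, some diaries fall on days when the study instructs the diet before an OGTT

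*Protocol*

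**What the plan says.** **Diary.** Section 8.12.1.2 asks for "3-day food diaries of the child's dietary intake at 3 month intervals during the first year of life and biannually thereafter". On timing it says: "The primary caretaker will be instructed to fill out the 3-day food diary directly prior to the next clinic visit". The reason given is "so that they can bring the completed record with them". The sentence takes the 6-month visit as its case, and no later text sets a different timing for older children.

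**Accelerometer.** Section 8.11 plans annual wear from age 5 of the "accelerometer for 7 consecutive days (including 2 weekend days) in order to generate adequate valid data". Families are mailed the device one month before the target visit and told to "begin using the device two days before the three day diet recording period and for two days after". On return: "All families will be asked to return the accelerometer at their next TEDDY visit". Mailing envelopes are mentioned only for families who forget to bring it.

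**OGTT.** Section 8.17.2 limits six-monthly OGTTs to children aged 3 or older who have had two or more autoantibodies at the same visit. Under the OGTT alert in Section 13.6.1 these children are "asked to undergo standard OGTT every six months at the time of their regular TEDDY visit". Section 9.2 adds: "Subjects will be instructed to eat a balanced diet in the days leading up to the OGTT". It gives no number of days.

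**The concern.** Two consequences follow from placing the diary against the visit.

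First, the wear window is defined by the diary, and two of its days come after the diary ends. If the diary ends the day before the visit and the device is handed over at the visit, those two days are lost. A family that follows every instruction then cannot supply the amount of data that Section 8.11 itself treats as adequate.

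Second, at an OGTT visit the diary covers days when the study is directing what the child eats. This happens only in multiple-positive children. Section 8.12.1.2 keeps diaries going after age 10 in single- and multiple-positive children so that diet can be related to progression to T1D. A difference in how diet is measured between these two groups bears directly on that analysis.

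**Working it through.** **Planned wear.** Inputs from Section 8.11: 2 days before the diary, 3 diary days, 2 days after. 2 + 3 + 2 = 7, which reproduces the planned figure.

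**Wear obtained.** Let g be the number of full days between the last diary day and the visit at which the device is returned. Full wear days = 2 + 3 + min(2, g).

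- g = 0 (diary on days -3 to -1, return on day 0): 2 + 3 + 0 = 5. Planned wear runs from day -5 to day +1, so the two later days fall on the visit day and the day after it.
- g = 1: 2 + 3 + 1 = 6.
- g = 2: 2 + 3 + 2 = 7.

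**Weekend days with g = 0** (wear on days -5 to -1):

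| Visit day | Wear days | Weekend days |
|---|---|---|
| Monday | Wed-Sun | 2 |
| Tuesday | Thu-Mon | 2 |
| Wednesday | Fri-Tue | 2 |
| Thursday | Sat-Wed | 2 |
| Friday | Sun-Thu | 1 |

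**Illustration of the cost.** The protocol gives no day-to-day correlation. For an assumed single-day intraclass correlation (ICC) of 0.3 to 0.5, the reliability of a d-day mean is d × ICC / (1 + (d - 1) × ICC).

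- d = 7: 2.1/2.8 = 0.75 to 3.5/4.0 = 0.88.
- d = 5: 1.5/2.2 = 0.68 to 2.5/3.0 = 0.83.

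**Diary and OGTT overlap.** Both run on six-month cycles. All children are seen every three months to age 4, and persistently positive children remain on that schedule (Section 8.2.1). The two cycles can therefore coincide or alternate. With diaries at 36, 42 and 48 months, an OGTT series starting at 36 months meets every diary if it continues without a break; one starting at 39 months (39, 45, 51) meets none. The overlap is real for the first kind of child and absent for the second. It never arises in infants, in antibody-negative children or in children who have only ever had one antibody.

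**The case against.** **On the accelerometer.** The protocol does not define the diary as ending the day before the visit, and a two-day gap would restore all seven days. The next TEDDY visit could also be read as a later one. These readings are possible but not natural. The device is mailed one month before the target visit, prompt return is rewarded, and the envelopes serve families who forget. Holding the device past the visit is not the stated plan.

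**On the OGTT overlap.** A reader might infer that diary days are OGTT preparation days in general, or that every later diary in a multiple-positive child is affected. The eligibility rule in Section 8.17.2 rules out the first. The second needs the two cycles to coincide, which the protocol does not state.

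A reader might also infer that the instruction will create a false association between diet and progression. A simulation with no true diet effect shows what that would take. It used 281 + 105 = 386 antibody-positive children (Section 10.3) followed for 10 years. Half were assumed multiple-positive, with 50% reaching T1DM in 5 years (the parent letter in Section 13.4), and single-positive children were assumed to progress at 2-4% per year. An assumed shift in recorded intake of 0.2 SD gave an unadjusted hazard ratio of 1.06-1.09 per SD and 3-8% false positives at the 0.01 level; 0.3 SD gave 1.09-1.13 and 9-19%. Stratifying the same data by single versus multiple positivity gave 1.00 and 0.8-1.4%.

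The protocol gives no basis for a shift of that size. It names no food, amount, direction or number of days. Section 10.1 plans multivariate as well as univariate models, and the choice of covariates may sit in an analysis plan not seen here. So a false association is not shown. What stands is that diet may be recorded differently by antibody status. Stratification removes the contrast between groups, but it cannot recover habitual intake that was never recorded. Any remaining bias among multiple-positive children has not been quantified.

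**Conclusion.** The accelerometer conflict holds. Sections 8.11 and 8.12.1.2 cannot all be followed for the annual collection from age 5: 5 full wear days are obtained instead of 7, and a Friday visit misses the two-weekend-day requirement as well. This rests on the diary ending the day before the visit and on the device being returned at that same visit. Monday to Thursday visits still contain two weekend days.

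The OGTT point holds in a narrow form. It concerns children aged 3 or older with two or more autoantibodies, at visits where a diary and an OGTT coincide. The number of preparation days is not stated, so overlap with all three diary days is likely but not certain. It is a reason to protect the diet-progression analysis, not evidence that the analysis is biased by a known amount.

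**What to change.** **Accelerometer (Section 8.11).** Choose one:

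- Families keep the device until the two days after the diary are complete, then return it in the mailing envelope already provided for late returns. Cost: slightly later return.
- At accelerometer visits only, the diary ends at least two full days before the visit. Cost: a slightly longer gap between the diary and its review.

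**Diaries before an OGTT (Section 8.12.1.2).** Flag each diary kept directly before an OGTT visit. Stratify or adjust the diet-progression analyses by single versus multiple positivity, and repeat them without the flagged diaries. Cost: one derived variable from visit data and one sensitivity analysis with fewer records. OGTT preparation is unchanged.

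Moving every diary a week or more ahead of the visit is not needed. It exceeds the two-day gap that the accelerometer requires. It would also change the instrument late in a 2004-2024 collection, after diaries in children who are not persistently positive had been stopped beyond the 10-year visit, so later records would differ in method from earlier ones.

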## 8.12.2. TEDDY Book

At the 3 month clinic visit, primary caretakers (usually mothers) will be introduced to the TEDDY Book. This is a notebook that is to be used by the primary caretaker to record events in their child's life that are of interest to the study. Primary caretakers are instructed to write down things such as when foods are introduced in their child's diet, use of food and vitamin supplements, medications, vaccinations, length and weight history of the child, illnesses and symptoms of the child, doctor's visits and hospitalizations, and life events of the child. The primary caretakers will be asked to bring in the TEDDY book to each clinic visit. At each visit, study personnel will go over the book with the primary caretaker and extract pertinent information using standardized study forms. The TEDDY book the primary caretaker first receives will be used up until the age of 2 years. After that, a more age-appropriate book will be distributed.

### 8.12.3. Infectious/Immunization Questionnaires and Interviews

At each clinic visit when the child is 3, 6, 9, 12, 15, 18, 21, 24, 27, 30, 33, 36, 39, 42, 45 and 48 months of age information on infectious illnesses and immunizations that occurred since birth or the last visit will be recorded. At 4 years of age and beyond information on infectious illnesses and immunizations will be collected every three months from those children who have been deemed persistent autoantibody positive; information on infectious illnesses and immunizations will be collected from all other subjects on a biannual basis beginning at 4 years of age. At 3 months, this will be done by a standardized interview. At subsequent visits, this will be done by extracting the information from the TEDDY book (see above).

## 8.12.4. Psychosocial Questionnaires and Interviews

## 8.12.4.1. Background

Genetic screening for disease risk raises a number of psychosocial and ethical issues. Genetic screening of children is particularly controversial when there is no available intervention to prevent the disease. (Weber, 1997; American Academy of Pediatrics, 2001; Johnson, 2001; Roth, 2001; Roth, 2002; Ross, 2003). Human subject consent procedures also require participants to be informed of the costs and benefits, including the psychosocial costs and benefits, of any study protocol. Since the TEDDY protocol will require the longitudinal study of infants at increased genetic risk for diabetes, in the absence of any known effective intervention to prevent the disease, the psychosocial impact on families who agree to participate must be addressed.

The psychosocial components of the TEDDY protocol are designed to: (1) assure participants are appropriately informed and supported during their study participation; (2) assess the psychosocial impact of study participation on families; (3) examine the role of psychosocial stress as a potential trigger for type 1 diabetes; and (4) identify family characteristics that discriminate study completers from study drop-outs.

## 8.12.4.2. Informing and Supporting Families During the Study

The literature suggests that individuals understand risk information best if both a categorical descriptor or label and a numerical risk estimate are provided (Kong et al., 1986; Shaw and Dear, 1990). In a previous study with mothers of infants at increased genetic risk for TIDM, we provided both a label and a numerical estimate of an infant's diabetes risk. We then examined the accuracy of mothers' estimates of infant risk approximately 4 weeks and 4 months after risk notification. Mothers who recalled both the label and a numerical estimate were more likely to be accurate about their infant's actual risk (Carmichael et al., 2003).

Based on these findings, TEDDY parents will be informed about the implications of their child's positive genetic test result-using a standard protocol: both a label (e.g., increased risk for diabetes) and a numerical estimate (e.g., 2 in 100 infants) will be used. If the child shows evidence of persistent autoimmunity, a standard protocol will be used to inform parents of the presence of persistent autoimmunity and its associated increased risk for T1DM in the child.

Each study site will specify procedures to promote participant retention as part of its study protocol. Since sites may differ in terms of participant needs (e.g., proximity of study assessment sites) and human subjects study requirements, these issues will be addressed in a site-specific manner. Each site's procedures will include, but not be limited to: contact information of friends or family members who are likely to have contact information for the participating families in years to come; evidence that the parents understand the nature of the study procedures and the length of time commitment required; procedures designed to minimize study procedure burden (e.g., use of distraction procedures and lidocaine-prilocaine - EMLA - cream prior to blood draws in the infant; reimbursing travel costs); procedures designed to maximize study procedure comfort and convenience (e.g. food record forms designed for ease of use; availability of study assessments as part of usual well-baby visits or in the evenings, on weekends, or at home); and procedures designed to thank and support participants for their efforts (e.g., birthday cards for infant and parents, small thank you baby gifts, educational or health information re the child's growth and development).

Since the nature and availability of psychological resources will vary across sites, these procedures will be specified by each site and will include a protocol for assessing whether a family wishes psychosocial support and if needed, how this support will be provided.

